7.2. Pharmacokinetic Assessments

The pharmacokinetics (PK) of psilocin (the major active metabolite of psilocybin) will be investigated following self-administration of a single dose of a whole organic psilocybin mushroom.

The PK profile of psilocin will be assessed in plasma on Study Day 1. Blood samples will be processed and analyzed for concentrations of psilocin by a validated method. On Study Day 1, participants must self-administer the psilocybin mushroom in a fasted state and will remain fasted for a minimum of 4 hours following the administration of study drug.

The specific collection times for PK blood samples are outlined below.

Predose:

- Up to -30 minutes before study drug administration

Post Dose:

- 30 minutes / 0.5 hours (\pm 2 mins) post dose
- 60 minutes / 1.0 hour (\pm 5 mins) post dose
- 90 minutes / 1.5 hours (\pm 5 mins) post dose
- 120 minutes / 2 hours (\pm 5 mins) post dose
- 4 hours (\pm 15 mins) post dose

CONFIDENTIAL

- 8 hours (± 15 mins) post dose

7.3. Premature Termination of the Trial

The Investigator has the right to terminate this trial at any time. If the trial is terminated, the Investigator is to promptly inform the study participants and the Institutional Review Board (IRB) and will arrange appropriate follow-up. If the trial or study is discontinued, all procedures and requirements pertaining to the archiving of documents will be observed. Study materials will be treated in accordance with federal and local regulations.

8. SAFETY ASSESSMENTS

8.1. Adverse Events

AEs and SAEs will be noted at each study visit. Participants will be queried to determine if anything has changed in their health status since the last visit (following Study Day 1), using non-leading questions. [For AE collection and reporting requirements, see [Section 10](#) of the protocol.]

8.2. Vital Signs

Participant vital signs, including blood pressure (systolic/diastolic), heart rate, respiratory rate, pulse oximetry and body temperature, will be assessed at each study visit.

Vital signs should be measured after the participant has been sitting in a relaxed manner for at least 5 minutes. Blood pressure measurements will be obtained with the participant in a sitting position.

8.3. Clinical Laboratory Assessments

Pregnancy Test: A urine pregnancy test for female participants of childbearing potential will be performed at Screening and on Study Day 1, prior to administration of the study drug.

Drug and Alcohol Tests: A qualitative rapid urine drug and an EtG urine test will be performed to test for recent alcohol consumption at Screening, on Study Day 1, prior to administration of the study drug and at the EoT visit.

- *Clinical Laboratory Testing:* Blood and urine sampling for clinical laboratory assessments will be performed at the study site or closest available facility. However, a urine sample, for urinalysis, only will be collected at the Screening visit.

- Results from the blood and urine tests will determine eligibility during the Screening Period.

Urinalysis results will include color, appearance, specific gravity, pH, protein, glucose, ketones, occult blood, leukocyte esterase, nitrite, bilirubin, urobilinogen. If clinically warranted, reflex testing to assess aberrant results (e.g., for a positive leukocyte esterase result) may be done at the discretion of the investigator.

Blood analyses will include a complete blood count for hematology parameters along with serum electrolytes, a metabolic profile and liver enzyme and renal function tests for blood chemistry parameters.

Table 3- Hematology Parameters

White blood cell count (WBC)	Red blood cell count (RBC)
WBC Differential count	Mean corpuscular volume (MCV)
Hemoglobin	Mean corpuscular hemoglobin (MCH)
Hematocrit	Mean corpuscular hemoglobin concentration (MCHC)

Table 4- Chemistry Parameters

Glucose	Alkaline phosphatase (ALP)
Total bilirubin	Lactose dehydrogenase (LDH)
Blood urea nitrogen (BUN)	Aspartate aminotransferase (AST/SGOT)
Creatinine	Alanine aminotransferase (ALT/SGPT)
Sodium	Gamma-glutamyl transpeptidase (GGT)
Potassium	Prothrombin time
Serum calcium	Albumin
Magnesium	Total protein
Phosphate	Bilirubin
Carbon dioxide	

- The Investigator will use normal ranges provided by the central laboratory.

Epigenetic Analysis: DNA methylation will be measured in the lab of [name] at Arizona State University.

DNA will be extracted from saliva samples with a standard isolation kit (Qiagen, Hilden, Germany). Sample yield and purity will be assessed using fluorometric methods (Quant-iT™ PicoGreen™ dsDNA Assay Kits; Invitrogen).

Approximately 500 ng of DNA will undergo bisulfite treatment using the EZ-96 DNAm Kit (Zymo Research, Irvine, CA). DNAm will be quantified using the Infinium MethylationEPIC v2 BeadChip run on an Illumina iScanSystem (Illumina, San Diego, CA).

Raw IDAT files will be preprocessed in “R” with the minfi package⁵⁵. Data will be subjected to quality control analyses, which includes quantile normalization, checking for sex mismatches, and excluding low-intensity samples ($p < 0.01$). Data will be normalized and annotated with Illumina CpG site probe names. Using the R package EpiDISH (Epigenetic Dissection of Intra-Sample Heterogeneity, 3.8) RPC method, a proportion of estimated epithelial cells will be generated as a covariate in the statistical models.

8.4. Concomitant Medications and Therapies

Participants will take note of their concomitant use of alcohol, medications, and other drugs, psychotherapy, and health care use and provide this information to the study site staff at their scheduled study visits.

Information about all concomitant prescription, non-prescription (including recreational) and/or over-the-counter drugs and medications as well as herbal dietary supplements, other home remedies will be collected from Screening up to the day of the final, 3-month LTFU visit. The

information to be collected will include the drug/supplement, the reason(s) for use, the dates started and ended (or noted as 'ongoing' at the end of a participant's involvement in the trial), the dosage (if available) and the route of administration.

Medications (including those taken to treat AEs) will be recorded in the participant's medical record and on a concomitant medications electronic case report form (eCRF).

Information on participation in psychotherapy or any other medical intervention that occurs during the course of the participant's involvement in the trial will be recorded on a concomitant therapy eCRF.

8.5. Suicidal Ideation

The Columbia Suicide Severity Rating Scale (C-SSRS) is a clinician-administered measure of suicidal behavior devised to detect potential suicidal thoughts or behaviors during a clinical trial (Posner 2007). It consists of a "Baseline" form that assesses lifetime suicidal ideation, intensity, and behavior, and a form for assessing current suicidal ideation and intensity. The C-SSRS consists of a series of questions and can be administered via face-to-face interview or over the telephone. The C-SSRS is a detailed interview, but the full interview is needed only if the initial screening questions about suicidal ideation and behavior are positive. The screening questions should be completed for every participant and as needed if a participant is showing any signs of being suicidal. For management of suicidal thoughts, see Section 10.3 Risk Mitigation.

9. RISK OF PARTICIPATION

9.1. Risks of Screening, Study Procedures, Assessments, and Measures

Measurements of blood pressure, body temperature, and heart rate, respiration rate and pulse oximetry will be taken during the trial to assess study drug effects and monitor participant safety. Participants may experience mild discomfort from having blood pressure assessed. Submitting to a full medical examination also may cause discomfort or psychological distress. Since medical examinations are required to establish eligibility for the study, it cannot be omitted from the protocol.

Participants also may have minor discomfort from phlebotomy procedures to collect blood samples for clinical laboratory evaluations and PK profiling, respectively.

Providing a saliva sample is considered an easy procedure and at worst may cause the participant to temporarily feel a sense of dry mouth.

Psychological assessments will be obtained through interviews or self-assessments. Because these interviews require individuals to discuss their condition, they may prove upsetting for some. Because psychiatric interviews and discussion of symptoms from life-threatening illness are used during screening, they cannot be avoided. The Investigator and trained staff have experience working with people with life-threatening illness, and they will seek to reduce anxiety and distress during these interviews.

The Investigator and study site staff (and the institution) will take all reasonable measures to maintain patient confidentiality and protect all personally identifiable and personal health information. Nonetheless, no guarantee can be made that there will not be a data breach or that information about the participant's involvement in this trial will not be disclosed.

9.2. Risks of Psilocybin

The risks of psilocybin mushrooms have been characterized in small clinical trials, including among individuals with anxiety, depression, and life-threatening illness (Goodwin 2022, Lowe 2021, Ross 2021, Griffiths 2016, Ross 2016). In systematic reviews of clinical trials with psilocybin mushrooms, the most common adverse effects reported were transient anxiety, headache, nausea or purging, psychological discomfort, physical discomfort, and autobiographical hallucination (Anderson 2020, Muttoni 2019). Vomiting was reported in one study (Griffiths 2016). Psilocybin also increased blood pressure and heart rate.

No SAEs have been reported for clinical studies involving psilocybin. These clinical trials typically employed one or two high doses of psilocybin but also included strong psychological support for participants both prior to and after dosing which may have supported integration and improved the safety profile.

9.3. Risk Mitigation

The Investigator will address a number of risks by enrolling participants without contraindicating conditions, including psychotic disorders and major medical conditions affecting the heart or lungs, etc. Participants who pose a major suicide risk also will not be enrolled in the study.

Untoward psychological reactions to psilocybin mushrooms will be dealt with by preparing participants for the subjective effects of the substance, and by self-administering the single dose of the psilocybin mushroom under observation by trained facilitators during the Study Day 1 visit who will be able to help address any anxiety or paranoid feelings the participant may experience.

Participants will be informed of the effects that psilocybin mushrooms might have on driving, and they will be advised to avoid driving for a minimum of 24 hours after study drug administration on Study Day 1. Participants will arrange rides home after Study Day 1 with a trusted adult companion. In addition, the same, or another, adult will stay with the participant overnight at their residence.

Potential reproductive risks will be mitigated by restricting enrollment to women who are not pregnant or lactating, and by requiring women of childbearing potential to undergo pregnancy testing prior to study drug administration during Screening and on Study Day 1 and use a highly effective form of birth control until Study Day 30 / EoT visit during the trial.

All study participants will be issued a 'study participant identification wallet card' that indicates that they may test positive for drugs of abuse (i.e., psilocybin) because they are participating in this clinical trial. The wallet card will include the telephone number for a 24-hour hotline and contain contact information for the Investigator and the IRB, along with the study National Clinical Trial Registry number. The investigator will remind participants that they may still be cited or face penalties for erratic driving and the card will not mitigate this penalty.

CONFIDENTIAL

All participants' protected health information will be stored in locked files or on secure computer servers and managed in accordance with patient confidentiality procedures pertaining to electronic systems.

The Investigator will discuss with participants the perceived stigma ascribed to psilocybin mushrooms use and to consider the degree to which friends, family, or other people within the community might respond if they observe or learn about the participant's psilocybin mushrooms use.

9.4. Criteria for Termination or Suspension of the Study

The study will be fully enrolled and completed as planned unless one or more of the following criteria are satisfied that require temporary suspension of the study.

- New information regarding the safety or efficacy of the study drug indicates a significant change in the known risk/benefit profile for the drug, such that the risk is no longer acceptable for subjects participating in the study.
- Significant violation of Good Clinical Practice (GCP) that compromises the ability to achieve the primary study objectives or compromises subject safety.
- Study-specific criteria for suspension of the study:
 - The study will be paused if:
 - One participant experiences any of the following during the treatment phase of the trial starting at the time of study drug administration and through Study Day 30/ EoT, even if the participant prematurely discontinued further involvement in the trial:
 - A CTCAE Grade 3 – 5 toxicity which is possibly or probably related to study treatment,
 - A suicide attempt,
 - A marked prolongation of QT interval (i.e., $QT \geq 450$ msec) over a series of 3 ECGs performed within 5-6 minutes,
 - A serious episode of psychosis as determined by the Investigator that requires immediate medical attention,
 - A severe, non-serious, AE possibly related to study treatment,
 - Two participants experience: One or more serious AE's possibly or probably related to study treatment.

The study might also be terminated by the sponsor for the following reasons:

- Slow patient enrollment,
- Data collected lacking quality,
- Poor adherence to protocol,
- Other findings that could lead to the study not meeting its objectives.

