4.3. Study Duration

The overall duration of the patient enrollment, treatment and follow-up phase of the trial is expected to last 9 months.

The duration of an individual's participation, that completes the trial (Screening through the 3-month posttreatment LTFU visit) will be between 3.5 to 4.0 months depending on the length of time a participant is in the Screening Period (up to 4 weeks). [In rare cases, a participant's total duration of involvement could extend beyond 4.0 months if the Screening Period is extended and/or if it is deemed necessary to continue to monitor an adverse event that did not resolve prior to the date of the 3-month posttreatment LTFU visit.]

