7.1.2 Pre-screening

Prospective participants may be interviewed by telephone to determine whether they might be suitable candidates to participate in the trial. At the start of the telephone interview, interviewees will provide verbal consent confirming that they are willing to share personally identifiable information and their personal health information to determine if they are likely to qualify for participation in the trial.

The pre-screening interview will include questions about the participant's medical and psychiatric history, current treatment, etc. The interviewees will be asked to provide responses to the 17-question Life Events Checklist for DSM-5 (LEC-5) and the 20-question PTSD Checklist for DSM-5 (PCL-5). Qualified study site staff will provide individuals that pass the pre-screening assessment with IRB-approved study information and consent materials for review and consideration.

- If the prospective participant is not eligible or not interested in taking part in the trial their personal information will be destroyed at, apart from the summary reason for ineligibility, which will be retained on the Screening Log. An eCRF will not be completed for candidates who are not enrolled.

Pre-screening information will be retained for candidates who provide specific permission via verbal consent for utilization and retention of this information and who and provide written informed consent to participate in the trial. The Screening Log will be completed to include the qualified participant's screening number. The Screening Log will be maintained and kept up-to-date and be available for review by the study site monitor.

Table 1

Schedule of Events

Activity	Pre-Screen	Screening Period		Day 1	Day 2	Day 4 (Virtual)	Day 8 (±1 day)	EoT Day 30 1 Month (±5 days)	LTFU 3 Month (±7 days)
		-30 - to -1 (Can be extended)							
			Prior to Study Day 1						
Pre-Screen Verbal Consent ¹	X								
LEC-5 [^]		X							
PCL-5 [^]		X							
Informed Consent		X							
Medical History	X	X		X	X	X	X	X	X
Concomitant Medications	X	X		X					
Eligibility Criteria	X	X		X					
Height / Weight ²		X					X	◆ ¹⁴	
Physical Exam ³		X					X	◆ ¹⁴	
Vital Signs ⁴		X		X	X		X	X	X
Urine Pregnancy Test ⁵		X							
Urine Drug / Alcohol Tests		X		X				X	X
Clinical Laboratory Tests ⁶		X ⁶		X			X	X	
Electrocardiogram ⁷		X		X			X		
Dispense/Collect Wearable		X						◆ ¹⁴	X
Saliva – Epigenetic Test				X			X	◆ ¹⁴	
Pharmacokinetic Test ⁸				X					
Administer Study Drug				X					

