If the participant prematurely discontinues from the trial, this will be their last study visit, unless there is an ongoing adverse event that will continue to be monitored until resolution or until the Investigator and Medical Monitor determine that no additional follow-up is medically necessary.

Otherwise, the participant will return to the study site for the final 3-month, LTFU, visit.

7.1.9 3-Month Long-Term Follow-up (LTFU) Visit

Approximately three months (i.e., 90 days) after Study Day 1, participants will return for the final, 3-month, Long-Term Follow-up (LTFU) visit. At this visit, a number of protocol-mandated tests, examinations, assessments and procedures will be done as described below.

- Inquire about any changes in the participant's health in a non-suggestive manner; however, any changes noted will not be considered adverse events unless they either were noted prior to the Study Day 30 / EoT visit and/or are considered to be 'possibly' or 'probably' related to study drug administration.
- Review concomitant medications/therapies (including psychotherapy and healthcare utilization).
- Perform a brief physical exam and obtain weight (only if Study Day 8 visit was not completed).

CONFIDENTIAL

- Obtain vital sign measurements.
- Obtain urine samples for:
 - Qualitative rapid urine drug screen.
 - Qualitative urine ethyl glucuronide (EtG) test to assess alcohol consumption.
- Review participant's use of health tracking wearable device and collect the device and download the data to the trial database.
- Administer and/or have the participant complete the following clinician rating scales and participant QoL and PRO instruments, respectively:
 - GAD-7
 - PHQ-9
 - BPI
 - NIH HEALS
 - C-SSRS
 - AUDIT
 - DUDIT

Upon completion of the 3-month, long-term follow-up visit and after the study site staff obtain all outstanding data, participants will have completed the study, except if there is an ongoing adverse event that the Investigator and/or Medical Monitor believe warrants continued monitoring until resolution or until it is determined that no additional follow-up is medically necessary.

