10.3. Adverse Event Collection

All AE and SAEs will be collected during the entirety of the participant's involvement in the trial. If a new AE/SAE is reported >30 days after Study Day 1 and up until the 3-month, LTFU visit, it will be recorded in the participant's medical record and the eCRF; however, unless the event is deemed to be possibly or probably related to the study drug, it will not be recorded as an adverse event.:

- Events related to planned treatments or physician visits for baseline conditions collected in the medical history will not be collected unless there is an exacerbation of the condition.
- Any AE leading to withdrawal from continued participation in the trial protocol will be collected throughout the study.
- All AEs related to changes in psychiatric status will be collected throughout the study.

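### Section 9.4 ends every one-participant pause trigger at Study Day 30/EoT, so no single later drug-related event automatically pauses dosing, even if others are still undosed

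*Protocol*

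**What the plan says.** Protocol Section 9.4 makes completion the default: "The study will be fully enrolled and completed as planned unless one or more of the following criteria are satisfied". Under the study-specific criteria, one lead-in governs five events, any of which pauses the study when it occurs in a single participant:

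- a possibly or probably related CTCAE Grade 3-5 toxicity;
- a suicide attempt;
- confirmed QT prolongation;
- a serious psychotic episode;
- a severe, non-serious, possibly related AE.

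The lead-in limits all five to the period "starting at the time of study drug administration and through Study Day 30/ EoT". It adds that participants who left the trial early are still covered, which widens who counts but not for how long. A separate line pauses the study when two participants have related SAEs; its own wording states no window.

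Safety collection runs longer. Section 10.3 says of new events reported more than 30 days after dosing and up to LTFU that "unless the event is deemed to be possibly or probably related to the study drug, it will not be recorded as an adverse event", so related ones are recorded as AEs. It also says "All AEs related to changes in psychiatric status will be collected throughout the study". Section 7.1.9 treats changes found at LTFU as AEs if they were noted before EoT "and/or are considered to be 'possibly' or 'probably' related to study drug administration".

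On timing, Section 4.1 allows at most 8 participants to be dosed together, out of up to 24. Section 4.3 states: "The overall duration of the patient enrollment, treatment and follow-up phase of the trial is expected to last 9 months", with 3.5 to 4.0 months per participant.

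**The concern.** A pause protects people who have not yet been dosed. The protocol accepts that drug-related harm may appear after Day 30, because it goes on recording such events for two more months. Yet the same event, judged related by the same Investigator on the same definitions, obliges a pause before EoT and not after it. No reason is given for stopping at Day 30.

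If dosing is staggered over several months, a related Grade 4 event in an early participant at Day 50 could come to light while later participants are waiting for a single 30 mg dose, and no one-participant rule would hold their dosing until the event had been reviewed.

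**Working it through.** The protocol gives no figure to reproduce here. The check has two parts: what still applies after EoT, and whether anyone could still be undosed by then.

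**What applies after EoT**

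- The five one-participant triggers have all lapsed.
- The new-information criterion in 9.4 has no time limit and is among the criteria that require suspension, but it applies only if the risk is judged no longer acceptable.
- The two-participant line needs a second participant with a related SAE.
- The DSMB (9.4.1, 11.1) may recommend suspension, and the Investigator may terminate (7.3). Neither is tied to a single event.

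**Inputs**

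- EoT at Day 30 ± 5 and LTFU at 3 months ± 7 days (Table 1), with 3 months taken as 90 days (7.1.9).
- 24 participants, at most 8 per session (4.1).
- 9 months overall, 3.5 to 4.0 months per participant (4.3).
- Assumption: 30 days per month. Study day is treated as days since dosing; the one-day difference does not matter.

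**Calculation**

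1. EoT falls at 30 - 5 = Day 25 to 30 + 5 = Day 35. LTFU falls at 90 - 7 = Day 83 to 90 + 7 = Day 97.
2. Time between the two visits: 83 - 35 = 48 to 97 - 25 = 72 days. Table 1 schedules no contact in this interval.
3. Minimum number of dosing sessions: 24 / 8 = 3.
4. Longest dosing span, if all 9 months are used: 9 - 4.0 = 5.0 to 9 - 3.5 = 5.5 months, about 150 to 165 days.
5. Dosing time left after the first participant's EoT: 150 - 35 = 115 to 165 - 25 = 140 days.
6. Dosing time left after the first participant's LTFU: 150 - 97 = 53 to 165 - 83 = 82 days.
7. Lower extreme: if all sessions fall within about 30 days, nobody is undosed when the first participant passes EoT, and the effect is nil.

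**Illustration on an assumed calendar.** Three sessions of 8, evenly spaced over 150 days, fall on days 0, 75 and 150. When the first group reaches EoT (Day 25 to 35), 24 - 8 = 16 are undosed. When it reaches LTFU (Day 83 to 97), 24 - 16 = 8 are undosed. Even spacing is an assumption, not something the protocol states.

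**How a late event would become known.** With no visit between EoT and LTFU, it would come from the participant hotline (9.5), from SAE reporting (10.4), from another spontaneous report, or from the LTFU visit itself. Events found only at LTFU matter for this point only if dosing spans more than about 83 to 97 days.

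**The case against.** The cut-off can be defended. A window for collecting AEs and a window for a one-event mandatory pause serve different purposes and need not match. Day 30 closes what 9.4 calls the treatment phase and agrees with the 30-day periods for contraception and for abstaining from other psychedelics. The drug is given once, and Section 2.3.2 describes excretion as complete within 24 hours. Under Section 10, both degrees of relatedness require a reasonable relation in time, which is harder to meet at Day 60 than at Day 6. This stands to the extent that the mismatch is a design choice and not a contradiction. It does not explain why an event that has been judged related should lose its power to pause dosing.

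A reader might infer that only discretionary routes are left after EoT. The text does not support that. The new-information criterion requires suspension once it is met, and most of the one-participant triggers also rest on an Investigator's judgement. The difference is the threshold: a single related event before EoT, against a judgement that the risk is no longer acceptable after it.

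Nor are late events left unhandled. SAEs go to the Investigator within 24 hours or by the next working day and are assessed with the Medical Monitor. Many late Grade 4-5 events would count towards the two-participant line, and the DSMB sees all the data. The DSMB Charter, which is not shown, may add criteria. Even so, 9.4 is where the protocol fixes the pause rule, and a stricter Charter would then differ from it.

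**Conclusion.** The point holds as an inexpensive improvement to consider. After EoT no single related event, including a related Grade 5 event, automatically pauses dosing, although such events are recorded until LTFU. This rests on the wording of 9.4 and is firm.

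The practical size is uncertain. It ranges from nothing, if dosing is completed within about 30 days, to a period of up to about 115 to 140 days after the first EoT during which dosing could continue. The upper figures assume that all 9 expected months are used. The protocol gives no rate of related events after Day 30, so no expected number of pauses or of affected participants can be claimed.

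A reader might also conclude that every late psychotic episode or suicide attempt should stop the trial, as it would before EoT, where 9.4 sets no relatedness condition for either. The documents do not support carrying that over unchanged: two further months in a PTSD population would bring in background psychiatric events, and Section 10.3 records other late events as AEs only when they are judged related.

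**What to change.** In Section 9.4, for as long as any participant remains to be dosed:

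- extend the triggers for possibly or probably related Grade 3-5 toxicity and for a severe, non-serious, possibly related AE through the 3-month LTFU visit;
- after EoT, apply the serious-psychosis and suicide-attempt triggers only when the event is judged possibly or probably related;
- leave the QT trigger as it is, since Table 1 schedules no ECG after Day 8;
- state that the two-participant related-SAE line runs through LTFU.

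Mirror the wording in the DSMB Charter. This takes a few sentences and needs no new visit, data item or committee. The cost is a slightly higher chance of a temporary pause, which the relatedness conditions keep in check.
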